1 **Hypolipidemic and Antioxidant Capacity of Spirulina and Exercise**

2 NCT number: NCT02837666.

3 Date: April 27, 2017

4 Responsible: [name] [name]

5 Autonomous University of Ciudad Juárez, México

6 e-mail: [contact]

7 **Abstract**

8 **Introduction:** In order to reduce cardiovascular diseases risk factors, a healthy  
9 diet must include dietary antioxidants from different sources (e.g. *Spirulina*  
10 *maxima*) and regular practice of exercise should be promoted.

11 There is a little evidence from animal studies that *Spirulina maxima* and exercise,  
12 decreases cardiovascular diseases risks factors. However, very few studies have  
13 proven the independent or synergistic effect of *Spirulina maxima* plus exercise in  
14 humans. Therefore, this study pretends to address this independent and  
15 synergistic effect in overweight and obese subjects participating in a systematic  
16 physical exercise program at moderate intensity on general fitness, plasma lipid  
17 profile and antioxidant capacity in overweight and obese subjects.

18 **Methods and analysis:** Through a randomized, double-blind, placebo-controlled,  
19 and a counterbalanced crossover study design, eighty healthy overweight, and  
20 obese subjects will be evaluated during a twelve-week isoenergetic diet,  
21 accompanied by 4.5 g a day of *Spirulina maxima* intake and/or a physical  
22 systematic exercise program at moderate intensity. Body composition, oxygen  
23 uptake, heart rate, capillary blood lactate, plasma concentrations of triacylglycerols,  
24 total, low and high-density lipoprotein cholesterol, antioxidant status, lipid oxidation,  
25 protein carbonyls, superoxide dismutase, catalase, glutathione, glutathione  
26 peroxidase, glutathione reductase, and paraoxonase will be assessed.

27 **Ethics and dissemination:** This study and all the procedures have been approved  
28 by the Universidad Autonoma de Ciudad Juarez Bioethics Committee. Moreover,

29 findings will be disseminated through peer-reviewed journals, national and  
30 international conferences.

31 **Trial registration number:** ClinicalTrials.gov: NCT02837666.

32 **Keywords:** Spirulina, dyslipidemias, oxidative stress, exercise, body fat,  
33 antioxidant.

#### 34 **Strengths and limitations of this study**

- 35 • Working with obese people, one of the main risk factors for cardiovascular  
36 diseases.
- 37 • This study can be extrapolated to different populations.
- 38 • Double-blind randomized controlled trial.
- 39 • There are not possible limitations to perform all the procedures described in  
40 the present paper.

#### 41 **Background**

42 Cardiovascular diseases (CVD) are the leading causes of death worldwide. Each  
43 year, 17.5 million people die because of these diseases . Dyslipidemias are a  
44 predisposing factor for CVD and are characterized by high concentrations of  
45 triacylglycerols (TAG), total cholesterol (TC), low-density lipoproteins cholesterol  
46 (LDL-c), and low concentrations of high-density lipoproteins cholesterol (HDL-c) .  
47 Besides dyslipidemias, oxidative stress (OxS) is also observed to rise in obesity ,  
48 , and it is also a predisposing factor for CVD .

49 As a way to reduce OxS, dyslipidemias and the CVD incidence, it has been  
50 proposed the intake of antioxidants that come from fruit and vegetable-rich diet or  
51 nutritional supplements, mainly by unprocessed foods . In this sense,  
52 cyanobacterium *Spirulina* is an important source of antioxidants, currently  
53 associated with cardiovascular protection properties .

54 For centuries, *Spirulina maxima* (*S. maxima*) has been cultivated and used as a  
55 nutritional supplement due to its content of amino acids and essential fatty acids,  
56 vitamin C, vitamin E, tocopherols, and phycocyanins . Recently, *S. maxima*  
57 studies have focused in verifying the biological activity of its components, including  
58 hypolipidemic and antioxidant effects . However, most studies have been  
59 conducted in animal models, with only a few studies focused on the biological  
60 effect in humans.

61 Furthermore, it is known that the practice of systematic physical exercise  
62 ameliorates CVD risks ; and it has been observed that also plays a role in OxS,  
63 especially physical exercise at high intensity (PEHI) . PEHI considerably  
64 increases general metabolism, oxygen uptake (VO2), and mitochondrial activity;  
65 thus increasing the reactive oxygen species (ROS) production. Instead, physical  
66 exercise of moderated intensity (PEMI) has the best protective effect exerted  
67 against CVD, mainly due to physiological adaptations, including the expression of  
68 antioxidant enzymes , which stop the formation and propagation of ROS, and  
69 improving redox status of the organism .

70 Algae and cyanobacteria have shown promising pharmacological properties  
71 providing health benefits and physical improvements . These effects are

72 attributed to their specific profile in bioactive compounds such as uncommon  
73 carotenoids, phenolic compounds, tocopherols besides their well-known content in  
74 vitamins and good quality proteins associated to their specific chemical structure  
75 and interaction with biological membranes .

76 In this sense, there is evidence that the cyanobacteria *Spirulina*, in addition to  
77 exercise, lower CVD risks. This was mainly observed in animal models .

78 However, no studies in humans under *Spirulina* and exercise experimental designs  
79 proving these benefits have been reported yet. Therefore, the ISESE study will  
80 analyses the independent and synergistic effect of the intake of *S. maxima* with a  
81 PEMI on general fitness, plasma lipid profile, and redox status in overweight and  
82 obese subjects.

### 83 **Methods/Design**

#### 84 **Hypothesis**

85 *Spirulina maxima* intake and a dosed physical activity program will improve lipids  
86 profile, general fitness and antioxidant status in overweight and obese subjects.

#### 87 **Objectives**

88 The ISESE project's main objective is to demonstrate that ingestion of *S. maxima*  
89 and a dosed physical activity program will decrease, both independently and  
90 synergistically, some CVD risks in overweight and obese subjects.

#### 91 **Outcome measures**

92 The primary outcome measure will be changes in the plasma lipid profile after a  
93 six-week of treatment (plasma TAG, TC, HDL-c, and LDL-c by using standardized  
94 enzymatic methods).

95 The secondary outcome measure will be changes in general fitness (maximal  
96 oxygen uptake ( $VO_2$  max), heart rate (HR), in onset blood lactate accumulation,  
97 and body fat mass); as well as changes in redox status (malondialdehyde (MDA),  
98 protein carbonyls, paraoxonase (PON1), superoxide dismutase (SOD), catalase  
99 glutathione (GSH), glutathione reductase (GR), and glutathione peroxidase (GPx).

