### 136 **Study design**

137 The study consists of *S. maxima* treatment during 14 weeks in a randomized,  
138 double-blind, placebo-controlled, and counterbalanced crossover design, aimed to  
139 eliminate inter-individual bias as well as boosting the reliability of final results;  
140 moreover, this design is commonly used in clinical trials in order to have better  
141 results and conclusions . Eligible participants (n= 80) will be divided into two  
142 groups, one with systematic practice of physical exercise (GEx) and other one  
143 without it (GNEx). The participants of each group will be randomized in equal  
144 proportions between *S. maxima* and placebo treatment, receiving either 4.5 g daily,  
145 in a non-transparent capsule during 12 weeks (6 weeks for the first treatment - 2  
146 weeks of washout period - 6 weeks for the second treatment) (Figure 1). Before  
147 any reported allergic reaction occurs, the treatment will be discontinued.

148 To maintain the overall quality and legitimacy of the clinical trial, code interruptions  
149 should occur only in exceptional circumstances when knowledge of the actual  
150 treatment is essential for further management of the participant. Investigators are  
151 encouraged to discuss with a Medical Advisor if they believe that unblinding is  
152 necessary. Unblinding should not necessarily be a reason for study  
153 discontinuation.

154 A student outside the research team will feed data into the computer in separate  
155 datasheets, so that the researchers can analyze the data without having access to  
156 information about the allocation treatments, storing all the participants' files in  
157 numerical order in a safe and accessible place. The participants' files will be stored  
158 for a period of five years after the end of the study.

159 The sample size was determined by using the statistical program G\*Power ,  
160 selecting a sample of 73 subjects with  $\alpha = 0.05$  and  $p = 0.85$ . This sample will be  
161 fixed to 80 subjects in order to anticipate the possible desertions from the study.

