## 162 **Maximum intensity tests**

163 Each subject will participate in four stress tests performed at maximum intensity  
164 (MIT) during the study; during MIT record, consumed O2 and produced CO2 will be  
165 taken by a gas analyzer (Cortex MetaLyzer® 3B, Germany), HR with a Polar H7  
166 sensor (Polar Electro, Lake Success, NY), and lactate in capillary blood samples  
167 will be assayed in a YSI 1500 Sport Lactate Analyzer (YSI Life sciences, OH,  
168 USA). The MIT protocol consists of using a cycle ergometer (Monark ergomedic  
169 828 E; Monark exercise AB, 105 Vansbro, Sweden) initiating with a workload of 50-  
170 75 W with increments of 15-30 W every 3 min for until 15 min or when the subject  
171 could no longer pedal more than 40 revolutions/min, finishing the test when  
172 reaching 90-100 % of the maximum HR reserve; MIT will not be valid for less than  
173 9 min (Figure 2). At the end of each increment load (3 min), capillary blood  
174 samples will be taken to determine lactate, and the physical perceived effort will be  
175 registered by using the Borg scale. Measurements of HR, glucose and blood  
176 pressure will serve to take care of the subject's health during each MIT.

177 Before the first MIT, subjects will decide to be in the GEx or GNEx, and then they  
178 will be divided randomly for the treatment, which consists in a daily dosage of 4.5 g  
179 of Spirulina or placebo in capsules which will be recommended the subjects to  
180 consume them before each meal every day during six weeks. The day after the  
181 first supplementation period, subjects will come back to perform the second MIT

182 with identical conditions to the first one. The third MIT will be performed after a  
183 washout period of two weeks to remove the effects of treatment and avoid any  
184 possible delayed effect of *S. maxima* in the organism. The last MIT will be  
185 performed after the second treatment with identical conditions to the previous three  
186 times. General fitness parameters will be measured the same day of all the MITs to  
187 have accurate results.

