### 238 **Statistical analysis**

239 To evaluate data distribution, normality and homoscedasticity tests on each of  
240 response variables analyzed will be conducted. In order to analyze differences  
241 between variables before and after the study and between the groups, an ANOVA  
242 test will be performed. To analyze possible associations between variables, a  
243 bivariate correlation analysis will be used. To analyze independence between  
244 variables, a multiple regression analysis will be performed. The software to use is  
245 GraphPad Prism 6.

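### Four unranked lipids form the primary outcome with no success rule or multiplicity control, and the stated alpha and power are tied to none of them

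*Combined protocol and SAP*

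**What the plan says.** All references are to the combined protocol and SAP.

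- **Outcome measures:** there is one primary outcome, change in the lipid profile, made up of four concentrations ("six-week of treatment (plasma TAG, TC, HDL-c, and LDL-c by using standardized"). No order, composite score or combining rule is given.
- **Objectives:** the aim is to lower, independently and "synergistically, some CVD risks in overweight and obese subjects". How many risks, and which, is left open.
- **Hypothesis and Background:** a direction of benefit is implied. The supplement "intake and a dosed physical activity program will improve lipids", and dyslipidaemia is described as high TAG, TC and LDL-c with low HDL-c ("LDL-c), and low concentrations of high-density lipoproteins cholesterol (HDL-c"). No rule requires a significant change to be in that direction.
- **Study design:** G*Power is cited for "selecting a sample of 73 subjects with" alpha 0.05 and p = 0.85, and the number is then "fixed to 80 subjects in order to anticipate the possible desertions from the study". No lipid, contrast, test, sidedness, effect size or SD is given.
- **Maximum intensity tests:** exercise is self-selected ("Before the first MIT, subjects will decide to be in the GEx or GNEx, and then they"). Only Spirulina versus placebo is randomised.
- **Statistical analysis:** to compare "between variables before and after the study and between the groups, an ANOVA" is planned. No primary variable, primary contrast or adjustment is named.

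**The concern.** At least three decision rules fit this text: success on any one lipid, success on all four, or success on one lipid chosen later. Their error rates and power differ widely. If the choice is made after the results are seen, a reader cannot tell a confirmed primary result from the best of four. A significant change in the harmful direction is not excluded from counting either. The power statement has the same gap, because 85% describes a different claim under each rule.

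**Working it through.** **Inputs.** From the documents: four primary lipids, alpha 0.05, p = 0.85, 73 subjects raised to 80. Assumed, because the documents are silent: p means power; tests are two-sided; one contrast per lipid; correlations between lipids from 0 to 0.9. Correlated cases are simulated with 200,000 runs of four t-tests at n = 73.

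**1. The plan's own figure.** 73 cannot be reproduced without an effect size, SD and test. Solving backwards for 85% power at two-sided 0.05 with 73 in total:

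| Test | Effect that gives 73 |
|---|---|
| Paired | standardised difference 0.355 |
| Two-group | standardised difference 0.71 |
| Three-group ANOVA | f = 0.395 |
| Four-group ANOVA | f = 0.42 |

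The same number fits very different designs. It is unverifiable, not wrong. The step to 80 implies (80 − 73)/80 = 8.75% desertions, a rate that is not stated.

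**2. Any one lipid at unadjusted two-sided 0.05.** If independent: 1 − 0.95⁴ = 0.185. For any correlation the figure lies between 0.05 and 4 × 0.05 = 0.20. Counting only changes in the beneficial direction, if independent: 1 − 0.975⁴ = 0.096, against a nominal 0.025.

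**3. All four required, each with 85% power.** If independent: 0.85⁴ = 0.522. Type I error stays at or below nominal.

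**4. Holm at overall 0.05.** The first step uses 0.05/4 = 0.0125. A two-sided test with 85% power at 0.05 and n = 73 has 68.2% at 0.0125 (73.2% if all 80 are analysed). This is the power for a lipid that responds alone. If all four respond and are independent, the chance of showing at least one is 1 − (1 − 0.682)⁴ = 0.990.

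| Correlation | Any lipid, false positive | Same, benefit direction only | Holm, false positive | All four, joint power | Holm, at least one when all respond |
|---|---|---|---|---|---|
| 0 | 18.5% | 9.6% | 4.9% | 52% | 99% |
| 0.5 | 16% | 7.9% | 4.3% | 64% | 92% |
| 0.7 | 13% | 6.5% | 3.7% | 69% | 87% |
| 0.9 | 9% | 4.7% | 2.6% | 77% | 80% |

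If HDL-c is negatively correlated with the other three, the benefit-direction figure is about 7% to 9%, depending on the strength of the correlation and on whether it is negative on the raw or the benefit scale.

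**5. One lead lipid at 0.05.** Power is 85% at 73 and 88% if all 80 are analysed, with no multiplicity cost.

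**The case against.** The strongest reply is that the plan speaks of a single primary measure, the lipid profile, and nowhere says that one significant lipid suffices. Read jointly, there is no type I inflation. This stands in part: the inflation is conditional, and its size rests on assumed correlations. It does not remove the gap, because no composite, global test or joint rule is defined and the analysis section refers to separate response variables.

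A second reply is that Holm looks costly at 68%. That is the lone-responder case. In the case where all four respond, Holm shows at least one lipid with 80% to 99% power, while the all-four rule succeeds with 52% to 77%. The two rules support different claims. All-four remains a legitimate choice if its power is stated.

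A third reply is that a rule for the Spirulina contrast alone is narrower than the stated objective, which also covers exercise and synergy. This is true, and it is a choice of primary contrast as well as of wording. It is justified because exercise is self-selected.

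Three stronger readings are tempting and are not supported:
- *The plan runs an 18.5% error rate.* The plan adopts no any-one rule, and 18.5% assumes independence.
- *The trial is too small, or 73 is miscalculated.* The inputs needed to test this are missing.
- *Four lipids by three effects (Spirulina, exercise, interaction) gives 46%.* That is 1 − 0.95¹². It needs twelve independent tests, each able to make the trial positive, and the documents do not say this.

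**Conclusion.** The concern holds as a missing decision rule. Four lipids are jointly primary with no ranking, success criterion or multiplicity control, and alpha and power are attached to no lipid or contrast. Under one rule the plan leaves open, the false-positive chance for a single contrast is about two to four times nominal (9% to 18.5% over correlations 0.9 to 0; bounds 5% to 20%). Under another, there is no inflation but joint power falls to about 52% to 77%.

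These figures rest on reading p as power, on two-sided tests and on the assumed correlations. The 68% for Holm is also two-sided; it would be about 66% if the 85% had been calculated one-sided. The plan should be changed, but data collection is unaffected.

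**What to change.** Before unblinding, for the randomised Spirulina-minus-placebo contrast at six weeks, write down one rule:

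1. **Lead lipid.** The investigators name one lipid, tested at two-sided 0.05. The other three are tested in a stated fixed order, or by Holm, only if it succeeds.
2. **All four under Holm.** Overall two-sided 0.05; success is at least one lipid significant after Holm.

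Under either rule, success requires a significant change in the beneficial direction: lower TAG, TC or LDL-c, or higher HDL-c. Requiring all four is an acceptable alternative if its joint power is stated.

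Restate the power sentence for the chosen rule, giving the lipid, contrast, sidedness, assumed difference and SD actually used. Report the self-selected exercise contrast and the Spirulina-by-exercise interaction separately, with confidence intervals. Do not attach the 0.85 to the interaction unless the sample size was calculated for it.

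**Cost.** The change is to protocol and SAP text, with no more participants if the stated power is accepted. Option 1 makes three lipids secondary. Option 2 has about 68% power for a lipid that responds alone (73% if all 80 are analysed), if the unadjusted two-sided test has 85% at 73. Restoring 85% for that case would take about 102 subjects before desertions. Under both options the primary claim covers Spirulina only, so it is narrower than the main objective.

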#### 100 **Participants' eligibility**

101 The inclusion criteria will be the age between 18 and 45 years old of both sexes:  
102 40 overweight (Body mass index (BMI): 25-29.9 kg/m^2) and 40 obese (BMI: >30  
103 kg/m^2). The subjects' exclusion criteria will be: drinking more than 100 mL of  
104 alcohol a week, taking drugs and/or food or vitamin supplements, having a chronic  
105 disease, or having a physical or electrocardiographic injury that prevents them from  
106 engaging in any regular physical exercise. The elimination criteria will be that the  
107 program subjects' attendance will be lower than 80% and/or 20% change in their  
108 body weight during study.

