#### 109 **Call to participation, ethics and safety procedures**

110 University students of Ciudad Juarez, Mexico with overweight and obesity will be  
111 personally invited to participate. Participants will be informed of the purpose of the  
112 study, and of the physical, clinical and biochemical procedures, benefits, physical  
113 intensity tests, and risks, all before beginning the clinical trial. To guarantee the

114 good physical and mental health of the participants at the beginning of all the  
115 studies, a medical clinical laboratory study examination and an electrocardiography  
116 at rest tests will be performed. Noting that investigators are trained in  
117 cardiopulmonary reanimation and that the laboratory has the necessary  
118 communication tools and channels to perform emergency procedures. This study  
119 and all the procedures have been registered appropriately in ClinicalTrials.gov  
120 database (NCT02837666) and approved by the Bioethics Committee of the  
121 Universidad Autonoma de Ciudad Juarez (Supplementary files). That participants'  
122 acceptance formalized by means of written informed consent and their anonymity  
123 and confidentiality will be strictly enforced. This study will be conducted in  
124 compliance with the principles of the Declaration of Helsinki.

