### 125 **Baseline measurements**

126 A day before beginning the treatment, subjects will visit the laboratory for baseline  
127 measurements. Body mass will be measured with subjects lightly dressed and  
128 barefoot in an electronic balance, and standing height with a stadiometer. Body fat  
129 percentage will be measured by plethysmography method (BodPod, USA), electric  
130 bioimpedance (in body 160, US), and by dual-energy X-ray absorptiometry (DXA)  
131 (Prodigy v6.8; GE Lunar, Milwaukee, WI) according to manual guidelines.  
132 Anthropometric parameters will be taken by the standardized method of the  
133 International Society for the Advancement of Kinanthropometry (ISAK), and  
134 according with ISAK Anthropometry Accreditation protocols . Researchers are  
135 standardized in handling equipment and procedures.

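### Women aged 18 to 45 are eligible, but neither pregnancy nor breastfeeding is an eligibility criterion, although the plan schedules a DXA scan, four maximum-intensity tests and a supplement course

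*Combined protocol and SAP*

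**What the plan says.** Participants' eligibility opens with "The inclusion criteria will be the age between 18 and 45 years old of both sexes", in two BMI groups of 40.

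The exclusions begin "The subjects' exclusion criteria will be: drinking more than 100 mL of" alcohol a week. They continue with drugs and food or vitamin supplements, and end with chronic "disease, or having a physical or electrocardiographic injury that prevents them from" exercising regularly. Elimination during the study follows if the "program subjects' attendance will be lower than 80% and/or 20% change in their" body weight.

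The section on the call to participation, ethics and safety adds, for the start of the "studies, a medical clinical laboratory study examination and an electrocardiography" at rest. The stated purpose is to secure good physical and mental health. The physical exercise protocol adds a health assessment and activity questionnaires (PAR-Q and YOU), meant to rule out physical obstacles to exercise.

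The scheduled procedures are as follows:

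- **Baseline measurements**, the day before treatment begins: body fat by plethysmography, by electrical "bioimpedance (in body 160, US), and by dual-energy X-ray absorptiometry (DXA").
- **Maximum intensity tests:** "Each subject will participate in four stress tests performed at maximum intensity".
- **Study design:** two six-week periods separated by a two-week washout, with a crossover between Spirulina and placebo.
- **Physical exercise protocol:** the exercise group also trains five days a week, two of them at 70-90% of heart rate reserve.

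**The concern.** The exclusion list decides who enters. Pregnancy and breastfeeding are not alcohol use, drug or supplement use, chronic disease, or an injury that prevents exercise. Applied as written, the list admits a pregnant student with a qualifying BMI. She would then have an X-ray scan and repeated tests to near-maximal heart rate, and would take a supplement for six weeks. Nothing in the eligibility text requires anyone to ask about her status first.

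What is at stake is participant safety at entry. The safety argument about X-ray and maximal exertion concerns pregnancy. For breastfeeding, the point is narrower: the plan gives the supplement and does not say whether a breastfeeding woman may enrol.

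**Working it through.** No figure in the plan bears on this point, so there is nothing to reproduce. The check compares each rule that could keep a pregnant woman out with the procedures she would otherwise undergo.

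**Rules that might apply**

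| Rule and section | Names pregnancy or breastfeeding? | Could it act before the baseline DXA scan and first maximal test? |
|---|---|---|
| Age and sex (Participants' eligibility) | No; both sexes, 18 to 45 | Yes, but it admits her |
| Alcohol, chronic disease, injury or ECG exclusions (same section) | No | Yes, but they do not describe pregnancy |
| Drugs and food or vitamin supplements (same section) | No | Only by accident, if she takes one; not if she is unaware of the pregnancy |
| Attendance below 80% or 20% weight change (same section) | No | No; both build up during the study |
| Medical and laboratory examination, resting ECG (ethics and safety procedures) | No pregnancy check named | Possibly; its content and its order relative to the scan are not given |
| Health assessment and questionnaires (physical exercise protocol) | Not as far as the text shows | Possibly; the section does not say whether the non-exercise group completes them |
| Heart rate, glucose and blood pressure during each maximal test (Maximum intensity tests) | No | No; measured during the test |

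**Procedures that follow enrolment**

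1. DXA is listed among the baseline measurements with no exception.
2. Four maximal tests are assigned to every subject, in both the exercise and the non-exercise group. Each finishes at 90-100% of heart rate reserve.
3. The crossover lasts 6 + 2 + 6 = 14 weeks. Each completer takes Spirulina in one of the two six-week periods.

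**Comparison.** No row is a stated pregnancy or breastfeeding criterion. The rows that might catch a pregnancy do so incidentally, and they act at entry. The text therefore leads from eligibility to an X-ray scan and maximal exertion without an explicit check between them.

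**The case against.** The strongest reply is that the plan is not without safeguards. It has a medical and laboratory examination, an ECG, a health assessment with questionnaires, and DXA done to manual guidelines. Any of these may in practice include a pregnancy question. The laboratory panel, the questionnaire items and the manual are not reproduced, and the consent form and supplementary files were not available to check. It would therefore be wrong to say that nothing would stop a pregnant woman from being scanned. What remains is that the eligibility section is complete as it stands and does not list pregnancy or breastfeeding, and that none of the other screens is described as a pregnancy check.

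Four stronger readings are tempting, but the documents do not support them.

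- **A distorted Spirulina effect.** The plan says "The primary outcome measure will be changes in the plasma lipid profile after a" six-week course, so a reader might infer that a lipid shift in pregnancy would bias the contrast. The documents give no size for such a shift, and treatment order is randomised 1:1, so the shift is not systematically aligned with Spirulina. In an equally weighted within-person mean of 80, one woman carries weight 1/80 = 0.0125. A between-period shift of d in her moves the contrast by d/80, in a direction set by her randomised order. That is a small added noise.
- **An expected number of pregnancies.** The documents give neither the number of women nor a pregnancy rate. A count of new pregnancies over 14 weeks would also miss the main exposure, since the only explicitly scheduled DXA scan is at baseline.
- **Repeated X-ray exposure.** Body fat mass is a secondary outcome, and fitness parameters are measured at every maximal test. The plan does not say which of the three body-fat methods is repeated, so further DXA scans are an inference.
- **Exclusion of women using hormonal contraception.** The drug exclusion is undefined. Reading it to cover contraceptives, and then inferring a higher chance of pregnancy among those enrolled, is speculation.

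**Conclusion.** The point holds as an omission in the eligibility criteria, on grounds of participant safety. As written, a pregnant woman aged 18 to 45 with a qualifying BMI may be enrolled for a baseline DXA scan, four maximal tests and, if she completes, six weeks of Spirulina.

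The size cannot be expressed as a number of participants from these documents, and it is probably small. The case rests on the nature of the procedures and the low cost of closing the gap. It does not rest on any effect on the primary analysis.

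The conclusion assumes that the eligibility section is the operative list and that no pregnancy criterion stands in the consent or supplementary material. If one does, the remaining task is to bring the eligibility section into line with it.

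**What to change.** In Participants' eligibility, make pregnancy and breastfeeding status an explicit criterion. State in the ethics and safety section that this status is established as part of the pre-study examination already planned, and that the examination precedes both the DXA scan and the first maximal test. Then reconcile the eligibility section with the ethics and safety, Baseline measurements and Maximum intensity tests sections, so that all four describe the same entry requirement and the same order of events.

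How a pregnancy arising during the 14 weeks is handled is for the sponsor and the ethics committee to set. The plan should state what they decide.

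The cost is a line of eligibility text, one item in an examination that is already scheduled, and the loss of very few candidates. The design and the analysis do not change.
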